2.2 AMG 334 Background

AMG 334 is a human monoclonal immunoglobulin (IgG2) against the CGRP receptor. AMG 334 binds to the CGRP receptor complex with high affinity (K_d of 20 pM) and competitively and reversibly blocks the binding of the native ligand, CGRP. AMG 334 functions as a CGRP receptor antagonist.

The potential mechanisms of action of CGRP receptor antagonists involve components of the trigeminal-vascular system and include normalization of CGRP-induced vasodilation, reduction of CGRP-induced neurogenic inflammation, and inhibition of pain transmission at the trigeminal ganglion and trigeminal nucleus (Durham, 2004; Poyner, 1992; Wang et al, 1995; Zimmermann et al, 1996). The site of action for AMG 334 will be predominantly restricted to the periphery due to AMG 334's physical size and structure (antibody). While it is not definitively known whether the CGRP receptors that are relevant for migraine lie within or outside of the blood brain barrier, the following scientific evidence argues strongly for a predominant role for peripheral CGRP in the generation of migraine:

- 1) CGRP-induced migraine headaches via intravenous (IV) infusion are most likely initiated through peripheral CGRP receptor signaling systems.
 - a. Migraine can be initiated by IV infusion of peripherally restricted CGRP peptides in migraine patients (Lassen et al, 2002).
 - b. CGRP is a 37-amino acid peptide (molecular weight [MWt] >3700 daltons). It most likely has limited brain penetration across the blood brain barrier (MWt cut off for brain penetration is ~ 500 daltons).
 - c. CGRP peptide has a short plasma half -life [mean plasma $T_{1/2}$ ~11 min in man (Kraenzlin et al, 1985)].
- 2) The physical and chemical properties of the CGRP-receptor antagonists olcegepant and telcagepant suggest that their site of action is likely to be in the periphery.
 - a. Olcegepant is a peptidic IV CGRP-receptor antagonist that has a molecular weight (MWt 870 daltons) that is greater than the upper limit for blood brain barrier penetration with low oral bioavailability (Rudolf et al, 2005).
 - b. A positron emission tomography (PET) study showed minimal brain penetration of telcagepant and low central receptor occupancy (4-10%) at the clinically efficacious dose of 140 mg (Connor et al, 2009; Ho et al, 2010; Hostetler et al, 2013). This degree of receptor occupancy would be unlikely to produce a functional effect.

Furthermore, in a large clinical study, a higher dose of 300 mg was not more efficacious than the 150 mg dose, suggesting that the treatment effect was saturated at a lower dose of 150 mg, which has little to no evidence of brain receptor occupancy ([Connor et al, 2009](#)).

- 3) Antagonist mechanisms typically require much higher receptor occupancy (>60%) to produce a pharmacodynamic (PD) effect resulting in efficacy ([Grimwood and Hartig, 2009](#)).

Given the likely peripheral activity of AMG 334 and its mechanism of action, it is unlikely that it will impact the treatment of aura, which is considered a central phenomenon ([Eikermann-Haerter et al, 2012](#)).

The preclinical toxicology data were generated in cynomolgus monkey as it is the only laboratory species in which AMG 334 had suitable binding and functional activity. There were no significant findings in the toxicology studies that would predict a risk to human subjects. The no-observed adverse effect level (NOAEL) was the maximum dose evaluated in the 6-month Good Laboratory Practice (GLP) toxicology study, 150 mg/kg subcutaneous (SC). There were no significant effects on electrocardiogram (ECG) parameters, blood pressure (BP) or respiration rate in the single dose cardiovascular study in cynomolgus monkeys.

The safety and PK of AMG 334 have been evaluated in three phase 1 studies that administered a single SC dose up to 210 mg, multiple doses up to 140 mg in healthy male subjects, and multiple dose studies of 21 mg and 140 mg in male and female migraine subjects.

Preliminary PK data are available from all subjects in the single dose first-in-human study. AMG 334 exposure increased more than dose proportionally at doses from 1 to 70 mg SC and increased approximately dose proportionally from 70 to 210 mg SC in healthy subjects. The median time of maximum observed concentration (t_{max}) ranged from 4 to 11 days within the dose range of 1 to 210 mg SC. There was no apparent difference in PK results between the healthy subject cohorts and the migraineur cohort.

In preliminary PK results from healthy subjects in the multiple-dose study, the observed mean area under the curve (AUC)_{0-28d} accumulation ratio at all 3 dose levels (21, 70, and 140 mg) after 3 monthly SC administrations was < 2, which is consistent with the dosing frequency and half-life of monoclonal antibodies.

Refer to the AMG 334 [Investigator's Brochure](#) for additional information.

2.3 Rationale

Migraine prophylaxis in chronic migraine is an area of large unmet medical need, with existing therapies not fully efficacious or poorly tolerated. While a variety of medications are used off-label for prophylaxis of chronic migraine, only onabotulinumtoxinA is approved for this indication. CGRP receptor antagonism represents a novel approach to migraine therapies. Results from the AMG 334 phase 2 study (Study 20120178) in subjects with episodic migraine demonstrated that the 70 mg dose resulted in statistically significant and clinically meaningful reductions in monthly migraine days at week 12 compared with placebo (70 mg: -3.40 vs Placebo: -2.28; Difference: -1.12; $p = 0.02$). Neither the 7 mg nor the 21 mg dose was associated with statistically significant reductions in monthly migraine days. The 70 mg dose produced statistically significant improvements in multiple secondary and exploratory outcome measures, including the 50% responder rate, monthly headache days, and monthly migraine-specific medication treatment days, while neither the 7 mg nor the 21 mg dose resulted in improvements in these measures. Exposure-response analyses over a large range of PK exposures indicate that 70 mg is the lowest dose that results in efficacious concentrations (Lenz et al, 2015; Sun et al, 2015). This study is designed to assess whether a CGRP receptor antagonist is safe and well tolerated in subjects with chronic migraine.

Rationale for AMG 334 Open-label Treatment Dose

A dose of AMG 334 70 mg was originally chosen for this phase 2 study based on the demonstration that this dose and higher doses have been generally well tolerated in phase 1 studies and that this dose is predicted to result in near complete inhibition of the peripheral CGRP receptor for a month. To ensure optimal efficacy is achieved with AMG 334, a higher dose, 140 mg, is currently being evaluated in the double-blind placebo-controlled parent study in chronic migraine (Study 20120295) as well as in a phase 3 study in Episodic Migraine (Study 20120296) and efficacy data are being collected. Based on the AMG 334 phase 2 data in Episodic Migraine, the open-label dose of AMG 334 is being increased in this study to 140 mg to provide additional 6-month and one-year safety data.

The no observed adverse effect level from preclinical toxicology studies was determined to be the high dose, 150 mg/kg SC twice weekly, corresponding to a maximum concentration (C_{max}) of 2620 $\mu\text{g/mL}$, and AUC_{0-7d} of 15300 $\mu\text{g}\cdot\text{day/mL}$. This is 275-fold and 296-fold higher than the observed mean C_{max} and AUC_{0-28d} , in humans after the third

dose of the repeated monthly SC administration of 70 mg and 111-fold and 129-fold higher than the observed mean C_{max} and $AUC_{0-28 \text{ day}}$ after the third monthly subcutaneous administration in humans of 140 mg, after correcting the different dosing frequency in cynomolgus monkeys and humans.

Based on the clinical data generated to date, it is expected that multiple doses of AMG 334 up to 140 mg will be well tolerated in subjects with migraine. AMG 334 has been administered at single doses up to 210 mg SC and 140 mg IV and at doses up to 140 mg SC administered monthly for 3 months in migraine subjects, and in healthy subjects at doses of 280 mg SC administered on day 1 followed by 210 mg SC administered on days 29 and 57. Refer to the AMG 334 [Investigator's Brochure](#) for details.

The ability of AMG 334 to inhibit CGRP receptors in humans was evaluated by inhibition of the DBF increase induced by topical application of capsaicin. This capsaicin-induced DBF model has been used to demonstrate proof of pharmacological activity for CGRP antagonists (eg, telcagepant, olcegepant) ([Sinclair et al, 2010](#)). Based on the results of the study with AMG 334, a dose of 70 mg is predicted to result in near complete inhibition of the peripheral CGRP receptor for a month. The plasma concentration achieved at 70 mg is approximately 10 fold higher than the 90% effective concentration (EC_{90}) from the DBF model and is sustained for greater than 28 days ([Figure 1](#)). The correlation between the DBF model and clinical efficacy in migraine prophylaxis has not been established with AMG 334 although clinical efficacy has been demonstrated in acute migraine treatment for telcagepant (a small molecule CGRP antagonist) at doses with concentrations approximately 2 - 4 fold higher than EC_{90} from the DBF model studies ([Connor et al, 2009](#); [Ho et al, 2008](#); [Sinclair et al, 2010](#)).

Figure 1. Predicted Capsaicin-induced Dermal Blood Flow (DBF) Inhibition (Left) and AMG 334 Exposure (Right) for the Phase 2 Doses

[figure not shown]

Figure legends: Lines in figures are median predicted DBF inhibition as percent of maximum inhibition (Left) and time courses by dose for AMG 334 concentration (Right). Estimated mean maximum inhibition in DBF response from phase 1 study is approximately 93%.

2.4 Clinical Hypotheses

The clinical hypothesis is that long-term exposure of AMG 334 will be safe and well tolerated in subjects with chronic migraine. In the CHU substudy, it is hypothesized that users will be able to administer a full dose of AMG 334 comparably using either the PFS or **prefilled** Al/pen. No formal hypotheses will be tested.

3. EXPERIMENTAL PLAN

3.1 Study Design

This is a multicenter, open-label study designed to assess the long-term safety and efficacy of AMG 334. Subjects who complete the 12-week double-blind treatment phase of the AMG 334 20120295 parent study and meet all AMG 334 20130255 eligibility criteria will be enrolled into the study. Enrollment should occur within 14 days after the parent study's week 12 visit. Subjects who enroll in the AMG 334 20130255 study will end the AMG 334 20120295 study and will not participate in the parent study safety follow-up visit.

All subjects who have not yet enrolled in the study will receive open-label AMG 334 140 mg every month (QM) SC for 13 months. Subjects who are already enrolled in the 20130255 study will increase the open-label dose from 70 mg QM to 140 mg QM at the first available opportunity at either week 4, 8, 12, 16, 20, 24, or 28 visits. Subjects who have already completed the week 28 visit will continue to receive 70 mg QM.

All subjects will receive open-label AMG 334 QM SC for 13 months followed by a 12-week safety follow up visit (16 weeks after the last dose of investigational product [IP]).

Investigational product (ie, AMG 334 70 mg or 140 mg) will be dosed QM, SC.

The overall study design is described by a [study schema](#) at the end of the protocol synopsis section.

The study endpoints are defined in [Section 10.1.1](#).

3.2 Number of Sites

It is anticipated that approximately 60 sites across North America and Europe will participate in the study. The same sites that participate in the parent study will be utilized for the study. All sites in the US, Sweden, and Germany may participate in the CHU substudy.

3.3 Number of Subjects

Participants in this clinical investigation shall be referred to as “subjects”. Up to 651 subjects may participate in the study. Up to 80 subjects may participate in the CHU substudy.

The sample size justification is described in [Section 10.2](#).

3.4 Replacement of Subjects

Subjects who are withdrawn or removed from treatment or the study will not be replaced.

3.5 Estimated Study Duration

3.5.1 Study Duration for Subjects

The planned length of participation in the study for an individual subject is up to 16 months, which includes the 13-month open-label treatment phase and 3 month (12 weeks) safety follow-up after treatment phase.

3.5.2 End of Study

Primary Completion and End of Trial: The time when the last subject is assessed for evaluation in the study (ie, when the last subject completes the study, which includes the

safety follow-up visit after the last dose of investigational product, or is discontinued from the study).

4. SUBJECT ELIGIBILITY

Investigators will be expected to maintain a screening log of all potential study candidates that includes limited information about the potential candidate (eg, date of screening).

Before any study-specific activities/procedure, the appropriate written informed consent must be obtained (see [Section 11.1](#)).

4.1 Inclusion and Exclusion Criteria

4.1.1 Inclusion Criteria

- 101 Subject has provided informed consent prior to initiation of any study-specific activities/procedures
- 102 Completed the 12-week study visit and did not end IP early during the double-blind treatment period of the AMG 334 20120295 parent study, and is appropriate for continued treatment

4.1.2 Exclusion Criteria

- 201 Development of any unstable or clinically significant medical condition, laboratory or ECG abnormality following randomization into the parent study, that in the opinion of the investigator, would pose a risk to subject safety or interfere with the study evaluation, procedures or completion

Note: Any ECG abnormality noted by the central reader must be evaluated by the investigator to determine if the ECG finding is representative of an unstable or clinically significant medical condition.
- 202 Any subject who experienced an SAE in the parent study (AMG 334 20120295) for whom the investigator determined that there was a reasonable possibility that the event may have been caused by investigational medicinal product
- 203 In the opinion of the investigator, subject demonstrated poorly controlled hypertension following randomization into the parent study
- 204 Systolic blood pressure (BP) 160 mm Hg and/or diastolic BP 100 mm Hg or greater at screening/Day 1

If the systolic BP is > 160 mm Hg or diastolic BP is > 100 mm Hg when initially assessed, BP may be repeated 30 minutes after the initial measurement. BP measurements may only be repeated once after the initial measurement
- 205 Subject is currently or plans to participate in another clinical study during participation in this study
- 206 Subject who used excluded concomitant medications between week 8 and week 12 of the parent study
- 207 Pregnant (as confirmed by the week 12 urine pregnancy test of parent study) or breastfeeding, or is a female expecting to conceive during the study, including through 16 weeks after the last dose of investigational product

208 Female subject of childbearing potential who is unwilling to use an acceptable method of effective contraception during treatment with AMG 334 through 16 weeks after the last dose of investigational product. Acceptable methods of effective birth control include not having intercourse (true abstinence, when this is in line with the preferred and usual lifestyle of the subject), hormonal birth control methods (pills, shots/injections, implants or patches), intrauterine devices, surgical contraceptive methods (vasectomy with medical assessment of the surgical success of this procedure or bilateral tubal ligation), or two barrier methods (each partner must use one barrier method) with spermicide - males must use a condom with spermicide; females must choose either a Diaphragm with spermicide, OR Cervical cap with spermicide, OR Contraceptive sponge with spermicide

Female subjects not of childbearing potential are defined as any female who:

- Is post-menopausal by history, defined as
 - Age \geq 55 years with cessation of menses for 12 or more months, OR
 - Age < 55 years but no spontaneous menses for at least 2 years, OR
 - Age < 55 years and spontaneous menses within the past 1 year, but currently amenorrheic (eg, spontaneous or secondary to hysterectomy), AND with postmenopausal gonadotropin levels (luteinizing hormone and follicle-stimulating hormone levels > 40 IU/L) or postmenopausal estradiol levels (< 5 ng/dL) or according to the definition of "postmenopausal range" for the laboratory involved.
- OR
- Underwent bilateral oophorectomy OR
 - Underwent hysterectomy OR
 - Underwent bilateral salpingectomy

209 Likely to not be able or available to complete all protocol required study visits or procedures, and/or to comply with all required study procedures (eg, independent completion of electronic diary [eDiary] items) to the best of the subject's and investigator's knowledge

5. SUBJECT ENROLLMENT

Before subjects begin participation in any study-specific activities/procedures, Amgen requires a copy of the site's written Institutional Review Board/Independent Ethics Committee (IRB/IEC) approval of the protocol, informed consent form (ICF), and all other subject information and/or recruitment material, if applicable (see [Section 11.2](#)). All subjects must personally sign and date the IRB/IEC and Amgen-approved ICF before commencement of study-specific procedures.

The screening phase starts when the subject signs and dates the ICF and ends when the subject is enrolled or screen failed (does not meet all screening eligibility criteria, refer to [Section 4](#)). The screening phase must not begin prior to the completion of all week 12 procedures in the AMG 334 20120295 parent study and must be completed within 14 days following the week 12 procedures in the parent study. Amgen may grant approval in cases for which additional time is required to confirm eligibility.

Subjects are considered eligible for participation once they have completed week 12 procedures in the parent study and meet all OLE study eligibility criteria. Subjects will be considered enrolled once they have received at least one dose of IP. The investigator is to document the date of enrollment in the subject's medical record and on the enrollment CRF.

Investigators may re-test laboratory values within the allowed screening window (within 14 days after the week 12 visit of the parent study). Reasons for a re-test may include:

- Laboratory value(s) out of range for unclear reasons
- The subject has a medical condition that can be resolved prior to the re-test attempt.

Subject numbers for this study will be an 11 digit number; the first 3 digits will be 255 and the remaining 8 digits will match the last 8 digits of the 11 digit number assigned by IVR System in the parent study. This number will be used to identify the subject throughout the clinical study and must be used on all study documentation related to that subject.

A subject who is determined to be ineligible must be registered as a screen fail in the IVR/IWR System.

6. TREATMENT PROCEDURES

6.1 Classification of Product and Medical Devices

The Amgen investigational product used in this study is AMG 334.

For subjects participating in the CHU substudy, Amgen investigational product used is AMG 334 either in a PFS or prefilled AI/pen.

6.2 Investigational Product

The double-blind treatment assignments from the parent study will remain blinded after subjects are enrolled into the OLE study until the primary analysis of the 20120295 study is conducted.

6.2.1 Amgen Investigational Product - AMG 334

Amgen investigational product will be manufactured and packaged by Amgen Inc. and distributed using Amgen clinical study drug distribution procedures. Amgen investigational product is also referred to as “study drug.”

For subjects in Study 20130255, AMG 334 will be supplied in 5 mL clear glass vials containing 1 mL of 70 mg/mL AMG 334 formulated with [CC] mM sodium acetate, [CC] % (w/v) sucrose, [CCI] % (w/v) polysorbate [C], at pH [CC].

Subjects randomized as part of the CHU substudy will be supplied with a sterile, single use, preservative free solution for SC injection in either two PFS or two **prefilled** Al/pens each containing 1 mL AMG 334 at a concentration of 70 mg/mL formulated with [C] mM sodium acetate, [CC] % (w/v) sucrose, [CCI] % (w/v) polysorbate [C], pH [CCI].

Detailed information regarding the storage and preparation of investigational product will be provided separately in the Investigational Product Instruction Manual (IPIM).

6.2.1.1 Dosage, Administration, and Schedule

Amgen investigational product (ie, AMG 334 70 or 140 mg) will be dosed QM, SC.

The quantity, start date, start times, injection site, stop date, and box number of investigational product are to be recorded on each subject’s case report form (CRF) when the site administers the IP. If a subject is enrolled in the CHU substudy, the box number provided to the subject and information obtained at telephone visits should be recorded by the site on each subject’s CRF, as described in [Section 7.2.1.16](#).

Overdose with this product has not been reported.

Investigational product will be administered by authorized investigational site study staff as the last procedure after all other study visit procedures have been completed. The one (for 70 mg dose) or two injections (for 140 mg dose) will be administered into the anterior abdominal wall, upper thigh, or upper arm. The injection site location should be the same if two syringes are used. During the CHU substudy, the site will provide IP to the subject to self-administer (two injections using either PFS or Al/pens) on the following day. The injection site location should be the same for both injections. For further details regarding self-administration procedures, the Instructions for Use (IFU) should be consulted.

Subjects should be observed for approximately 30 minutes after IP administration on day 1.

Please refer to specific instructions provided in the IPIM for additional information.

6.2.1.2 Rules for Withholding or Restarting Investigational Product

Investigational product doses are fixed and will not be adjusted for individual subjects during the study.

At any time during the study, the investigator may discontinue investigational product administration for any subject who experiences a severe or life-threatening adverse event reported by the investigator to be related to investigational product. Refer to [Section 9](#) for details regarding adverse event reporting.

End of investigational product and early discontinuation from investigational product are to be registered in the IVR/IWR System.

6.3 Hepatotoxicity Stopping and Rechallenge Rules

Subjects with abnormal hepatic laboratory values (ie, alkaline phosphatase [ALP], aspartate aminotransferase [AST], alanine aminotransaminase [ALT], total bilirubin [TBL]) and/or international normalized ratio [INR] and/or signs/symptoms of hepatitis (as described below) may meet the criteria for withholding or permanent discontinuation of Amgen investigational product or other protocol-required therapies as specified in the Guidance for Industry Drug-Induced Liver Injury: Premarketing Clinical Evaluation ([US FDA, 2009](#)).

6.3.1 Criteria for Permanent Discontinuation of Amgen Investigational Product due to Potential Hepatotoxicity

Amgen investigational product will be discontinued permanently and the subject should be followed according to the recommendations in [Appendix A](#) (Additional Safety Assessment Information) for possible drug-induced liver injury (DILI), if ALL of the criteria below are met:

- TBL > 2x upper limit of normal (ULN) or INR > 1.5
- AND increased AST or ALT from the relevant baseline value as specified below:

Baseline AST or ALT value	AST or ALT elevation
< ULN	> 3x ULN

- AND no other cause for the combination of the above laboratory abnormalities is immediately apparent; important alternative causes for elevated AST/ALT and/or TBL values include, but are not limited to:
 - Hepatobiliary tract disease
 - Viral hepatitis (eg, Hepatitis A/B/C/D/E, Epstein-Barr Virus, cytomegalovirus, Herpes Simplex Virus, Varicella, toxoplasmosis, and Parvovirus)

- Right sided heart failure, hypotension or any cause of hypoxia to the liver causing ischemia.
- Exposure to hepatotoxic agents/drugs or hepatotoxins, including herbal and dietary supplements, plants and mushrooms
- Heritable disorders causing impaired glucuronidation (eg, Crigler-Najjar syndrome) and drugs that inhibit bilirubin glucuronidation (eg, indinavir, atazanavir)
- Alpha-one antitrypsin deficiency
- Alcoholic hepatitis
- Autoimmune hepatitis
- Wilson's disease and hemochromatosis
- Nonalcoholic Fatty Liver Disease including Steatohepatitis (NASH)
- Non-hepatic causes (eg, rhabdomyolysis, hemolysis)

If an alternative cause for hepatotoxicity is identified or less stringent conditions developed than what are noted above, determine (based on patient population and/or severity of the hepatotoxicity or event) if Amgen investigational product should be withheld or permanently discontinued, as deemed appropriate for the safety of the subject.

6.3.2 Criteria for Conditional Withholding of Amgen Investigational Product due to Potential Hepatotoxicity

For subjects who do not meet the criteria for permanent discontinuation of Amgen investigational product outlined above and have no underlying liver disease, the following rules are recommended for withholding of Amgen investigational product and other protocol-required therapies:

- Elevation of either AST or ALT according to the following schedule:

Baseline AST or ALT value	AST or ALT elevation
Any	> 8x ULN at any time
Any	> 5x ULN but < 8x ULN for ≥ 2 weeks
Any	> 5x ULN but < 8x ULN and unable to adhere to enhanced monitoring schedule
Any	> 3x ULN with clinical signs or symptoms that are consistent with hepatitis (such as right upper quadrant pain/tenderness, fever, nausea, vomiting, jaundice).

- OR: TBL > 3x ULN at any time
- OR: ALP > 8x ULN at any time

Amgen investigational product should be withheld pending investigation into alternative causes of DILI. If investigational product(s) is withheld, the subject is to be followed according to recommendations in [Appendix A](#) for possible DILI. Rechallenge may be considered if an alternative cause for impaired liver tests (ALT, AST, ALP) and/or elevated TBL, is discovered and the laboratory abnormalities resolve to normal or baseline ([Section 6.3.3](#)).

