6.3.3 Criteria for Rechallenge of Amgen Investigational Product After Potential Hepatotoxicity

The decision to rechallenge the subject should be discussed and agreed upon unanimously by the subject, investigator, and Amgen.

If signs or symptoms recur with rechallenge, then Amgen investigational product will be permanently discontinued. Subjects who clearly meet the criteria for permanent discontinuation (as described in [Section 6.3.1](#)) should never be rechallenged.

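### As the text reads, the mandatory liver stop in Protocol Section 6.3.1 cannot be met by a subject whose AST and ALT were both at or above ULN at baseline, and Section 6.3.2 only partly covers the gap

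*Protocol*

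**What the plan says.** Section 6.3.1 requires three things together before the drug must be stopped for good:

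- total bilirubin (TBL) > 2x ULN or INR > 1.5;
- an enzyme rise, worded "AND increased AST or ALT from the relevant baseline value as specified below";
- "AND no other cause for the combination of the above laboratory abnormalities is immediately apparent".

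The table specifying the rise has one row: baseline < ULN, elevation > 3x ULN. The closing paragraph of the section deals with an identified alternative cause or a less stringent picture. It asks staff to "determine (based on patient population and/or severity of the hepatotoxicity or event) if Amgen investigational product should be withheld or permanently discontinued".

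Section 6.3.2 is addressed to a defined group: "For subjects who do not meet the criteria for permanent discontinuation of Amgen investigational product outlined above and have no underlying liver disease". For them, "the following rules are recommended for withholding of Amgen investigational product and other protocol-required therapies". Its four enzyme rows apply at any baseline: > 8x ULN; > 5x to < 8x ULN for 2 weeks or more; the same range when enhanced monitoring cannot be followed; and > 3x ULN with hepatitis signs or symptoms. Two further triggers stand on their own: "OR: TBL > 3x ULN at any time", and ALP > 8x ULN. No INR trigger is listed. After such withholding, "Rechallenge may be considered if an alternative cause for impaired liver tests" or raised TBL is found and the results have resolved.

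Section 6.3.3 requires unanimous agreement for any rechallenge. Its absolute bar is limited to "Subjects who clearly meet the criteria for permanent discontinuation" under Section 6.3.1.

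**The concern.** A baseline-dependent threshold that covers only one range of baseline leaves the rest without a threshold. Because Section 6.3.1 requires every criterion, a subject with both enzymes at or above ULN (including exactly at ULN) fails the enzyme criterion whatever happens later. The same on-study result is then a mandatory stop in a subject who started normal and a matter of judgement in one who did not.

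The documents do not exclude such subjects. Exclusion 201 sets no numeric AST/ALT limit; it turns on the investigator's opinion of abnormalities arising after parent-study randomization. Section 6.3.1 also does not say which baseline is meant, and SAP Section 6.3 defines two for safety data: before parent-study dosing and before day 1 of this study. Under the second, enzymes that rose above ULN during the parent study would themselves take the subject out of the mandatory rule. At stake are the mandatory stop and the absolute rechallenge bar, in a study whose primary objective is safety.

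**Working it through.** The plan states no figure to reproduce, so the check applies the two rules to the same results.

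**Conditions.** No other cause apparent, no underlying liver disease, no hepatitis symptoms, ALP at most 8x ULN, enhanced monitoring followed. Enzymes and TBL are in multiples of ULN. The two baselines are chosen for illustration.

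| On-study result | 6.3.1, both enzymes 0.8 at baseline | 6.3.1, both 1.2 at baseline | 6.3.2, either baseline |
|---|---|---|---|
| ALT 4, AST 2, TBL 2.5 | met | not met | not met |
| ALT 4, AST 2, TBL 1.5, INR 2.0 | met | not met | not met |
| ALT 6 for 1 week, AST 2, TBL 2.5 | met | not met | not met |
| ALT 9, AST 6, TBL 2.5 | met | not met | met |
| ALT 20, AST 15, TBL 6, INR 2.0 | met | not met | met |

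If hepatitis symptoms are present, Section 6.3.2 is met in all five rows, because every ALT exceeds 3x ULN.

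**Extent of the uncovered zone.** Take a grid of rule inputs:

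- ALT 3.5 to 20 in steps of 0.5: (20 − 3.5)/0.5 + 1 = 34 values.
- TBL 0.5 to 10 in steps of 0.5: 20 values.
- INR 1.0 or 2.0: 2 values. AST is held at 1.5.
- Total: 34 × 20 × 2 = 1360 combinations.

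Meeting Section 6.3.1 with normal baseline: at INR 2.0, all 34 × 20 = 680; at INR 1.0, TBL must be 2.5 or more, so 34 × 16 = 544. Sum 1224. With both baselines raised: 0.

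Of those 1224, the ones also missing Section 6.3.2 need TBL of 3 or less and ALT of 8 or less. TBL/INR combinations: 2 at INR 1.0 (TBL 2.5 and 3.0) plus 6 at INR 2.0 (TBL 0.5 to 3.0), so 8.

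- ALT above 3 to 5: 4 values × 8 = 32.
- ALT above 5 and below 8, short-lived: 5 values × 8 = 40.
- ALT exactly 8, which no row of the 6.3.2 table covers: 1 × 8 = 8.

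Total 80, and 80/1224 = 6.5%. With symptoms the count is 0. These counts describe the rules, not how often patients would land there.

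**One enzyme raised at baseline.** With AST 0.8 and ALT 1.2 at baseline and a rise confined to ALT, Section 6.3.1 is not met if each enzyme is matched to its own baseline. It is met if either baseline may serve. The text does not decide between the two.

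**Number of subjects.** The documents give no rate. As an assumption for scale only, 0.5% to 2% of up to 651 subjects with both enzymes at or above ULN gives 651 × 0.005 = 3.3 to 651 × 0.02 = 13.0. These would be subjects outside the rule, not expected liver cases.

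**The case against.** The strongest objection is that the single row may be an artefact of reading the PDF. A baseline column serves little purpose with one row, and a table that lost a row would look like this. That cannot be excluded. Against it, nothing marks a gap, and the next table, with the same headings, kept all four rows.

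The second objection is that other text already protects these subjects, and much of it stands. The closing paragraph of Section 6.3.1 makes permanent discontinuation available by judgement. Appendix A puts every subject with AST or ALT > 3x ULN under close observation, with repeat tests within 24 hours, a search for causes and a hepatology consult; retesting is every 24 hours when TBL > 2x ULN or INR > 1.5. INR is not in the routine panel, so the INR example mostly concerns a subject already being worked up. After withholding under Section 6.3.2, rechallenge is contemplated only when an alternative cause is found, which in practice comes close to the absolute bar. None of this is a mandatory permanent stop, and Section 6.3.2 leaves out subjects with underlying liver disease.

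Third, the parent study's liver eligibility limits are not in these documents and could bring the number affected to zero. That is fair, and it limits the weight of the point.

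A reader might infer that raised-baseline subjects have no liver rule at all, or that Section 6.3.2 helps them only once TBL exceeds 3x ULN. Neither is supported. The criteria in Section 6.3.2 are alternatives, so its enzyme rows need no bilirubin rise and its bilirubin trigger needs no enzyme rise.

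**Conclusion.** The gap is real as the text reads, and narrow. A subject with both AST and ALT at or above ULN at baseline cannot meet the mandatory stop, and so is not reached by the absolute rechallenge bar. Without symptoms or underlying liver disease and with ALP at most 8x ULN, the results under neither rule are AST/ALT > 3x to 5x ULN (or up to 8x if short-lived and monitored) combined with TBL > 2x to 3x ULN, or with INR > 1.5 and TBL at most 3x ULN. Outside that zone Section 6.3.2 recommends withholding. Subjects with underlying liver disease have only the judgement clause and Appendix A.

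Two stronger readings go too far. One is that a single raised enzyme is enough to lose the stop; that depends on how enzymes are matched to baselines, which the text leaves open. The other is that the 24-hour serious-event report for liver injury is lost as well. Appendix A ties that report to Section 6.3 as a whole, which leaves its reach unclear, and Section 9.1.2 separately names drug-induced liver injury as an example of a medically important serious event.

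The conclusion assumes that no table row was lost in extraction. The number affected is unknown and probably very small. This is a minor safety correction.

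**What to change.** First check the original page of Section 6.3.1 for a second table row. If there is none:

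- Add a row for baseline at or above ULN with a threshold that requires a real rise: a multiple of the subject's own baseline that also exceeds 3x ULN, with the multiple set by the sponsor's clinical team. A bare > 3x ULN would let a change from 2.9x to 3.1x ULN count, a ratio of 3.1/2.9 = 1.07. A baseline of 1.2x with ALT 4x ULN is a ratio of 4/1.2 = 3.3. Any multiple between those two ratios rejects the first and still catches the second.
- Keep the criterion that no other cause is apparent.
- State which pre-dose value is the relevant baseline, and whether each enzyme is compared with its own.

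The cost is one table row and one or two sentences in an amendment. No visit or routine test is added: AST, ALT and TBL are in the chemistry panel, and INR comes in through the Appendix A work-up. The downside is that a few more subjects may meet the mandatory stop.
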